#### **14 Analysis of other variables**

The proportion of subjects reaching the pre-defined, cumulative dose in each DM-101 treatment group is one of the secondary endpoints. It will be summarised using descriptive statistics.

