AIT involves repeated administration of the relevant allergen (via subcutaneous (s.c.) injection or orally/sublingually) for long periods of time, usually 3-5 years. Typically, AIT starts with a build-up phase, during which the allergen doses are progressively escalated, followed by a maintenance phase where a high, well tolerated, allergen dose is given regularly for a prolonged period. The better established and widely used forms of AIT include administration of natural allergen extracts. Despite its promising efficacy, AIT with natural allergens is associated with several limitations, including poor adherence due to the long duration of treatment, variable treatment responses because of the often-questionable quality of allergen extracts and concerns for serious side effects, such as severe allergic reactions (Roberts, 2018). The magnitude and duration of the AIT benefit seems to be related to the total (cumulative) dose of the administered allergen. When natural allergens are used, the maximum cumulative dose that can be achieved is restricted and requires a long treatment period to be delivered in a safe manner (Calderón, 2011; Penagos, 2018; Worm, 2018). To reduce the duration of s.c. AIT, various rush and ultra-rush dose escalation protocols have been successfully developed and applied in clinical practice (Cox, 2006; Calabria, 2013). These protocols include fast increase of the allergen doses, over a very short build-up phase, in order to induce quick desensitization and to facilitate early initiation of the maintenance phase. Maintenance treatment for several years is, however, still required to achieve a high cumulative allergen dose and long-lasting benefit (Calderón, 2011).

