Usually, FIH trials start with evaluation of single, ascending doses of the Investigational Medicinal Product (IMP), followed by multiple ascending dose evaluation until a safe and well tolerated dose range and dosing regimen are established. The targeted maximum dose is usually pre-defined in the study protocol, based on preceding non-clinical evidence. However, in the case of AIT products, assessment of the safety and tolerability of single doses does not necessarily provide appropriate information, as most AIT schedules include continuous dose escalation until a maximum tolerated or protocol-defined target (maintenance) dose is reached. The continuous dose escalation induces immunological changes, associated with allergen desensitization, that reduce the risk of allergic reactivity following subsequent dose administration, compared to the risk carried by single administration of the allergenic product, without prior exposure to it. To permit, therefore, appropriate evaluation of the safety and tolerability of DM-101, a repeat dose escalation regimen, previously employed in AIT protocols for pollen-driven respiratory allergies (Calabria 2013; Winslow, 2016), was included in the FIH study plan (protocol version 1.1). The FIH study was initiated in February 2020, but temporarily halted because of the Covid-19 pandemic on 17th March 2020, during the conduct of cohort 2.

During the conduct of the rapid, repeat dose escalation phase regimen included in cohort 2, safety findings were observed in all subjects dosed with DM-101. The findings did not meet the study's stopping criteria but indicated that the maximum tolerated dose of DM-101 is lower than initially anticipated. For this reason, the originally planned rapid dose escalation regimen has been amended (study protocol version 2.0). In the amended study protocol, a much slower and limited dose escalation is proposed, based on the findings from cohorts 1 and 2 of the study. This amended dosing regimen is expected to be well tolerated, but still capable of providing relevant information for further product development.

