### **Revised dose selection rationale for Cohorts 3 and 4**

Based on the safety findings from the initially conducted cohorts of this FIH trial and Desentum's latest laboratory data on the amount of biologically active Bet v 1 in commercially available birch pollen s.c. AIT products, it is considered important to continue this study with a DM-101 dosing scheme that carries low risk of induction of serious allergic reactions. To this end, the study design has been amended to include only 2 additional cohorts (cohorts 3 and 4) where DM-101 will be administered following a very slowly escalating repeat dose regimen, with doses starting from 30 ng, up to a maximum

of 300 ng. The rapid dose escalation over 2 consecutive days (Visit 2, Day 1 and 2) included in the original study protocol (version 1.1) has been omitted. Instead, a slow dose escalation that will take place over 5 bi-weekly dosing visits is proposed.

Dosing in both cohorts, 3 and 4, will start with administration of a single s.c. injection of placebo or 30 ng of DM-101 on Visit 2, followed by a single s.c. injection of placebo or 50 ng of DM-101 2 weeks later (Visit 3). Subsequently, in cohort 3 dosing will continue with single administration of placebo or 100 ng DM-101 on each of the Visits 4 to 6. In cohort 4, Visits 4 to 6 will include s.c. injections of placebo or increasing doses of DM-101 corresponding respectively to 100, 200 and 300 ng (Table 8). The doses of 200 ng and 300 ng will be administered as 2 and 3 s.c. injections of 100 ng respectively, with at least 30 min intervals between injections.

The starting dose of 30 ng has been selected because it was found to be safe and well-tolerated by the subjects who completed cohort 1 of this study. The subsequent 2nd dose of 50 ng and 3rd dose of 100 ng have been selected as modest steps of dose escalation in order to maximise safety. The 100 ng dose level has already been tested as the starting dose of the 4 subjects who received cohort 2 active treatment in this study; in these subjects, 100 ng DM-101 was not associated with the development of significant TEAEs or systemic allergic reactions. In cohort 3, 100 ng is the maximal planned dose that will be administered on subsequent visits until the end of the treatment phase. If this dosing scheme is well tolerated by the cohort 3 subjects, further dose escalation above 100 ng will be attempted in cohort 4 at Visit 4 (200 ng) and at Visit 5 (300 ng).

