**Table 8 Revised Study Cohorts - DM-101 Doses (ng) and Dosing Schedules\* - Protocol version 2.0**

		Cohorts	1 	2 	3	4
Visit 2	Day 1	1st injection	30	100	30	30
		2nd injection	-	250		
		3rd injection	-	500		
		4th injection	-	1,000		
		5th injection	-	2,500		
		6th injection	-	5,000 		
	Day 2	1st injection	-	(5,000) 		
		2nd injection	-	(10,000) 		
		3rd injection	-	(25,000) 		
		Day 1 & Day 2 Cumulative dose	30	(49,350)	30	30
Visit 3	Day 14	1 injection	-	(25,000) 	50	50
Visit 4	Day 28	1 injection	-	(25,000) 	100	100
Visit 5	Day 42	1-2 injections **	-	(25,000) 	100	200
Visit 6	Day 56	1-3 injections**	-	(25,000) 	100	300
		Total Cumulative dose	30	(149,350)	380	680

\*Acceptable Visit Windows:  $\pm 1$  day for Visit 3, and  $\pm 2$  days for Visits 4, 5 and 6.

\*\* In cohort 4, doses of Visits 5 and 6 are divided into 2 and 3 injections, respectively

Cohort 1 was completed according to the study protocol version 1.1

Cohort 2 was started according to the study protocol version 1.1 but dosing and recruitment were interrupted at Visit 2

Highest dose actually administered in cohort 2 before halt of study;

Never administered

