#### **2.1.2. Secondary Objective**

To determine the proportion of adult subjects with birch pollen allergy who reach the pre-defined, maximum admissible s.c. DM-101 dose in each dosing group.

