#### **2.2.2. Secondary Endpoints**

The number and severity of systemic allergic reactions in subjects receiving s.c. DM-101, compared to placebo.

The number and severity of local injection site reactions in subjects receiving s.c. DM-101, compared to placebo.

The proportion of subjects reaching the pre-defined, admissible dose in each DM-101 dosing group.

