## 3 Study objective(s)

The primary objective of the study is to evaluate the safety and tolerability of subcutaneous (s.c.) administration of DM-101 in adult subjects with birch pollen allergy. A secondary objective is to determine the proportion of study subjects who reach the pre-defined maximum admissible s.c. DM-101 dose in each dosing group.

An exploratory objective of the study is to evaluate the possible effects of repeated s.c. DM-101 dosing on immunological biomarkers in study subjects with birch pollen allergy.

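### SAP 14 analyses the proportion reaching the cumulative dose, but the only secondary objective is the proportion reaching the maximum admissible dose; in cohort 3 the two can differ

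*SAP*

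**What the plan says.** - **Objective.** Protocol 2.1.2 asks for the proportion of subjects "who reach the pre-defined, maximum admissible s.c. DM-101 dose in each dosing group". SAP 3 agrees: to "determine the proportion of study subjects who reach the pre-defined maximum admissible s.c. DM-101 dose in each dosing group". Neither document lists another secondary objective.
- **Endpoint.** Protocol 2.2.2 lists three secondary endpoints. The one that matches the objective reads "The proportion of subjects reaching the pre-defined, admissible dose in each DM-101 dosing group". The word maximum has dropped out, and cumulative is not there.
- **Analysis.** Protocol 10.10 and SAP 14 share one sentence: "The proportion of subjects reaching the pre-defined, cumulative dose in each DM-101 treatment group is one of the secondary endpoints". It is to be summarised descriptively. SAP 14 gives no target in ng, no analysis set and no denominator.
- **Doses.** Protocol 1.2.3 says "In cohort 3, 100 ng is the maximal planned dose that will be administered on subsequent visits". Table 8 ("Revised Study Cohorts - DM-101 Doses (ng) and Dosing Schedules") carries the total cumulative dose on its own row: 380 ng for cohort 3 and 680 ng for cohort 4.
- **Related output.** SAP 11 plans a summary of cumulative received dose and, separately, the numbers and percentages of subjects given each planned dose. SAP 21.1 has no table labelled for this endpoint, and SAP 17 declares no deviation from the protocol.

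**The concern.** The objective is about a dose level; the analysis is about a running total. No text in either document says they are the same thing. The background section does speak of a maximum total ("the maximum cumulative dose that can be achieved is restricted"), but that describes immunotherapy with natural allergens. For this trial the maximum in cohort 3 is given as 100 ng, and the total is a separate figure.

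A programmer who follows SAP 14 would therefore report a different quantity from the one the objective names. A cohort 3 subject who received 100 ng and then left for a reason unrelated to safety would be counted as not reaching the dose. With six active subjects per cohort, one such case moves the result by a sixth. If the definition is settled only after unblinding, the choice becomes post hoc.

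Two details are also open: whether reaching a dose means receiving it or tolerating it, and who is in the denominator when a subject is replaced.

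**Working it through.** **Inputs.** Doses at Visits 2 to 6 come from Protocol Table 8. Six DM-101 subjects in each of cohorts 3 and 4 come from Protocol 3.2. Replacement of subjects who leave for reasons other than a TEAE comes from Protocol 4.1, and step-down after a Grade 3 reaction from Protocol 9.3. Maximum dose is read as the maximum daily dose.

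**Table 8 totals reproduce.**
- Cohort 3: 30 + 50 + 100 + 100 + 100 = 380 ng; running totals 30, 80, 180, 280, 380.
- Cohort 4: 30 + 50 + 100 + 200 + 300 = 680 ng; running totals 30, 80, 180, 380, 680.

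Protocol 12 gives 710 ng as the most employed. That matches neither total, and the passages must be reconciled.

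**Dosing paths, with reach taken as received.**

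| Path | Cohort 3: ng | Max 100 / total 380 | Cohort 4: ng | Max 300 / total 680 |
|---|---|---|---|---|
| Stop after Visit 2 | 30 | no / no | 30 | no / no |
| Stop after Visit 3 | 80 | no / no | 80 | no / no |
| Stop after Visit 4 | 180 | **yes / no** | 180 | no / no |
| Stop after Visit 5 | 280 | **yes / no** | 380 | no / no |
| Complete | 380 | yes / yes | 680 | yes / yes |
| Miss Visit 3, then as scheduled | 330 | **yes / no** | 630 | **yes / no** |
| Miss Visit 4, then as scheduled | 280 | **yes / no** | 580 | **yes / no** |
| Miss Visit 5, then as scheduled | 280 | **yes / no** | 480 | **yes / no** |

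In cohort 3 the maximum is first given at the third of five dosings, at 180/380 = 47% of the total. A step-down after Visit 4 gives 30 + 50 + 100 + 50 + 50 = 280 ng, again yes / no. A step-down after Visit 5 gives 330 ng if the repeated level is 50 ng; Protocol 9.3 leaves that unclear when 100 ng was tolerated at Visit 4.

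**Direction.** On the received reading the cumulative rule can only equal or lower the proportion. Without ever receiving the maximum, the most a subject can get on the Table 8 levels is 30 + 50 + 50 + 50 + 50 = 230 ng in cohort 3 (below 380) and 30 + 50 + 100 + 200 + 200 = 580 ng in cohort 4 (below 680).

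**If reach means tolerated.** The cohort 3 step-down after Visit 4 becomes no / no, so the rules agree. In cohort 4, a Grade 3 reaction after the last Visit 6 injection leaves 680 of 680 ng received. If the cumulative dose is the received dose, as in SAP 11, that subject meets SAP 14 but not the objective.

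**Cohorts 1 and 2.** Cohort 1 has a single 30 ng dose, so maximum and total coincide: 4/4 under both. In cohort 2 none of the four DM-101 subjects started Day 2: 0/4 under both.

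**Size in cohort 3.** Let k DM-101 subjects stop after Visit 4 or 5 for a non-TEAE reason, with all others, including any replacements, completing.

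| Handling | Maximum rule | Cumulative rule | Gap | k = 1 | k = 2 |
|---|---|---|---|---|---|
| Not replaced | 6/6 | (6 − k)/6 | k/6 | 16.7 points | 33.3 points |
| Replaced, kept in denominator | (6 + k)/(6 + k) | 6/(6 + k) | k/(6 + k) | 14.3 points | 25.0 points |
| Replaced, dropped from denominator | 6/6 | 6/6 | 0 | 0 | 0 |

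**The case against.** The strongest reply is that the number is not lost. SAP 11 already promises the percentage of subjects given each planned dose, and the exposure table in SAP 21.1 is on the Safety set. On the received reading, the share given 100 ng in cohort 3 or 300 ng in cohort 4 could be read from it. SAP 14 also repeats Protocol 10.10 exactly, so the fault starts in the protocol. There are no hypotheses, the groups are tiny, and the dropouts in the calculation are supposed, since the documents give no dropout figure.

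All of that is true, and it limits the harm. It does not make the exposure table the endpoint: SAP 14 gives that status to the cumulative quantity, and nothing links SAP 11 to the objective.

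Three further points narrow the case:
- The objective never says daily. Read per injection, 100 ng is also the maximum in cohort 4, and stops after Visit 4 or 5 would differ there too. The daily reading is better supported: Protocol 1.2.3 and SAP 2 give a maximum of 300 ng, and Protocol 3.2 calls 200 ng a daily dose. It remains an assumption.
- Support for the tolerated reading is thin. The line "until a maximum tolerated or protocol-defined target (maintenance) dose is reached" concerns immunotherapy schedules in general and allows either target, and the similar text in Protocol 1.2.2 belongs to the replaced rush regimen.
- The Safety set keeps every dosed subject, so dropping a replaced subject would conflict with it. SAP 14, however, does not name that set.

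In the other direction, the size table counts only non-TEAE exits. On the received reading, a safety stop after Visit 4 or 5 in cohort 3 is discordant as well.

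**Conclusion.** The concern holds. The objective and the planned analysis name different quantities, no text reconciles them, and in cohort 3 they give different answers for any subject who stops after Visit 4 or Visit 5. One unreplaced case moves the proportion by 16.7 points and two by 33.3. The gap is zero if no such case occurs, or if replaced subjects are dropped from the denominator. Whether any subject is affected cannot be known from the documents.

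This rests on the Table 8 schedule, on the daily-dose reading and, for the size table, on reach meaning received. Cohorts 1 and 2 are unaffected. Cohort 4 differs on the received reading only if an earlier dose is missed and 300 ng is still given. No type I error or power is involved, and either proportion can be rebuilt from the data. The missing definition of reach, the analysis set and the denominator are gaps in detail that would not carry the point alone, but they should be closed in the same edit. It should be fixed because the analysis as written does not answer the only secondary objective.

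**What to change.** Before the cohort 3 and 4 code is broken:

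1. Rewrite SAP 14 so that the endpoint is the proportion of dosed DM-101 subjects in each cohort who reach that cohort's maximum daily dose in Table 8.
2. State whether reach means received, or received and tolerated.
3. State the analysis set and the denominator when a subject is replaced. The Safety set would keep a dosed subject who is later replaced.
4. Report completion of the full Table 8 cumulative dose as a separately labelled supportive line.
5. Name the SAP 21.1 table that carries both, and record the departure from Protocol 10.10 in SAP 17.
6. Align Protocol 2.2.2 and 10.10 with the objective at the next amendment.

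The code for cohorts 1 and 2 is already broken, but both rules give the same result there, so those data cannot favour one over the other.

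The cost is one paragraph in SAP 14, one line in SAP 17 and one small table, from data already collected for SAP 11 and SAP 16. The protocol wording can wait, since Protocol 11.4 sends essential changes through a substantial amendment that needs approval. A breakdown by reason for not reaching the dose is optional.

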#### **15 Analysis of exploratory variables / Immunological biomarkers**

Descriptive statistics and visualizations will be provided for Allergen-specific IgE levels (for components Bet v 1, Bet v 2, Bet v 4 and Bet v 6), and immunological biomarkers (such as IgG sub-classes and IgA). Bet v 1 and immunological biomarker results may be presented also in relation to the cumulative received dose for cohorts 3 and 4. Exploratory statistical analysis may be used to illustrate the association of dose received and biomarker levels, if feasible.

#### **16 Completion and premature discontinuation**

Completions and premature discontinuations will be tabulated and listed. The reasons for premature discontinuations will be presented.

## 17 Deviations from the analyses planned in the study protocol

No deviations of the statistical analysis plan are considered from the current protocol version (3.1).

## 18 Execution of statistical analyses

Statistical analyses will be performed by 4Pharma Ltd. according to the company's SOPs.

## 19 Hardware and software

Statistical analysis and preparation of tables and subject data listings will be performed with SAS® version 9.4 for Windows (SAS Institute Inc., Cary, NC, USA).

## 21 Appendices

### 21.1 Table and figure plan

#### 14.1 Demographic and Baseline Characteristics

Table 14.1.1	Disposition of subjects (All subjects)
Table 14.1.2	Analysis sets (ITT)
Table 14.1.3	Descriptive statistics of demographic variables (ITT)
Table 14.1.4	Descriptive statistics of background variables (ITT)
Table 14.1.5	Medical history (ITT)
Table 14.1.6	Prior and concomitant treatments (ITT)
Table 14.1.7	Concomitant treatments used to treat adverse events (ITT)
14.3	Safety data
14.3.1	Exposure
Table 14.3.1.1	Extent of exposure (Safety)
14.3.2	Adverse events
Table 14.3.2.1	Summary of Adverse events (Safety)
Table 14.3.2.2	Adverse events by SOC and PT (Safety)
Table 14.3.2.3	Adverse events by causality (Safety)
Table 14.3.2.4	Adverse events by severity (Safety)
Table 14.3.2.5	Serious adverse events (Safety)
Table 14.3.2.6	Adverse events leading to discontinuation (Safety)
14.3.3	Other safety variables
Table 14.3.3.1	Summary of systemic allergic reactions (Safety)
Table 14.3.3.2	Systemic allergic reactions by SOC, PT and grade (Safety)
Table 14.3.3.3	Systemic allergic reactions by SOC, PT and onset (Safety)
Listing 14.3.3.4	Tryptase results (Safety)
Table 14.3.3.5	Local injection site reactions by SOC, PT and grade (Safety)
Table 14.3.3.6	Local injection site reactions by onset (Safety)
Listing 14.3.3.7	Size of local injection site reaction compared to the dose of each injection
Table 14.3.3.8	Safety laboratory variables (Safety)
Table 14.3.3.9	Shift tables for change from baseline out-of-range laboratory values (Safety)
Table 14.3.3.10	Vital signs (Safety)
Table 14.3.3.11	Physical examination (Safety)
Table 14.3.3.12	Spirometry (Safety)
Table 14.3.3.13	Descriptive statistics for ECG parameters
Table 14.3.3.14	Summary of ECG interpretation
Figure 14.3.2.1	Safety laboratory variables (Safety)
14.3.3	Exploratory variables / Immunological biomarkers
Table 14.3.3.1	Allergen-specific IgE levels (ITT)

Table 14.3.3.2 Immunological biomarkers (ITT)

Figure 14.3.3.1 Allergen-specific IgE levels (ITT)

Figure 14.3.3.2 Immunological biomarkers (ITT)

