**Table 7. Summary of treatment-emergent adverse events in cohort 2**

Category	DM-101 (N=4) f n (%)	Placebo (N=1) f n (%)	Total (N=5) f n (%)
Any TEAE	56 4 (100.0)	2 1 (100.0)	58 5 (100.0)
IMP-related TEAEs	50 4 (100.0)	0 0 (0.0)	50 4 (80.0)
Severe TEAEs	0 0 (0.0)	0 0 (0.0)	0 0 (0.0)
Serious TEAEs	0 0 (0.0)	0 0 (0.0)	0 0 (0.0)
TEAE leading to discontinuation*	2 2 (50.0)	0 0 (0.0)	2 2 (40.0)

Abbreviations: TEAE = Treatment-emergent adverse event; n = the number of subjects with at least one TEAE; f = the number of TEAEs

\*One of the discontinued subjects had 2 reasons for discontinuation, both withdrawal of consent and 2 Grade 3 local injection site reactions after 2 injections of IMP.

Based on the findings of the interim analysis and in order to ensure the safety of the study subjects, the dose and dose escalation scheme for further cohorts were decided to be revised.

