## 7 Analysis sets

A subject classification document including a list of protocol deviations with a clinical classification of the deviations and the definition of the analysis datasets will be prepared and

approved after database lock before opening of the randomization code. For cohorts 1 and 2, subject classification was already done prior to opening of the randomization code of these cohorts for the interim analysis and report (documented in Desentum DM-101-C001 Subject Classification Final 18May2020.doc). The subject classification of cohorts 3 and 4 will be done after the database lock of the full database and prior to opening of the randomization code of these two remaining cohorts.

Three main analysis data sets were planned to be constructed. The intent-to-treat (ITT) data set was to include all subjects having received study medication and providing at least a minimum amount of relevant measurements. The safety data set was to consist of subjects having received at least one dose of study medication. The per protocol (PP) data set was to exclude all subjects from the ITT data set who meet any of the predefined criteria in the subject classification document.

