## 13 Analysis of safety variables

The primary endpoint of the study is the number of all treatment-emergent adverse events (TEAEs) in subjects receiving treatment with DM-101, compared to placebo. TEAEs will be MedDRA coded and tabulated by System Organ Class and Preferred Term. Occurrence of single Preferred Terms will be presented by cohort and treatment. In addition, TEAEs will be reported by causality and severity. Both subject and event counts will be summarized. Adverse events occurring prior to first administration of study drug will be listed.

The number and severity of systemic allergic reactions in subjects receiving treatment with DM-101, compared to placebo, will be presented in a similar manner as the TEAEs.

Systemic allergic reactions (SAR) are described with case narratives and will be graded per WAO classification and summarized by cohort and treatment. In addition, an overall summary of SARs by grade, causality, severity, seriousness, and concomitant/additional treatment given (yes/no) will be created. SARs by onset (dosing day and immediate vs delayed (>30 min from dosing)) will be summarized as well. Local injection site reactions (pain, tenderness, erythema/redness, induration/swelling) will be graded on a five-point (0 to 4) scale. These will be summarized by cohort and treatment and presented separately for each cohort (including by injection). Also, a summary by onset (immediate vs. delayed (>30 min from dosing)) will be given and the size of the measured skin reaction for all cohorts (using the collected precision) will be summarized by subject over time and compared to the dose of each injection.

Other safety variables include results from physical examination, vital signs, clinical laboratory values and spirometry. The results will be presented using descriptive statistics and visualizations by cohort, time point and treatment. For the laboratory assessments, all out-of-range values and their clinical significance (CS) (categories: low[CS], low[NCS], normal, high [NCS], high [CS]) will be summarized with shift tables for change from baseline. If feasible, also these parameters and changes from pre-dose to post-dose can be compared to the cumulative dose. Tryptase values will be listed by subject and time point (measured only for subjects with suspected grade 3 or higher systemic allergic reaction or anaphylactic shock).

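### Table 14.1.7 (treatments given for adverse events) is planned on ITT although the adverse event tables use the Safety set, and Table 14.1.2 cannot show a dosed subject left out of ITT

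*SAP*

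**What the plan says.** SAP section 7 and Protocol 10.5 define the sets in the same terms. Safety needs one or more doses. ITT needs dosing and also "providing at least a minimum amount of relevant measurements". The minimum is not stated; the set definitions are left to a subject classification document. For cohorts 3 and 4 that document is finalised after database lock and before the code is opened. For cohorts 1 and 2 it was finalised in May 2020.

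The table plan in SAP 21.1 then assigns the outputs as follows:

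- **ITT:** Table 14.1.2, "Analysis sets (ITT"; Table 14.1.3, "Descriptive statistics of demographic variables (ITT"; Table 14.1.4, "Descriptive statistics of background variables (ITT"; Table 14.1.5 (medical history); Table 14.1.6, "Prior and concomitant treatments (ITT"; Table 14.1.7, "Concomitant treatments used to treat adverse events (ITT"; and the IgE and biomarker outputs.
- **Safety:** exposure; all six adverse event tables (14.3.2.1 to 14.3.2.6); the three systemic allergic reaction tables; and the two injection site reaction tables (14.3.3.5 and 14.3.3.6).

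SAP section 10 promises separate summaries of medication used for adverse events but names no analysis set. SAP section 13 adds, for systemic allergic reactions only, that "an overall summary of SARs by grade, causality, severity, seriousness, and concomitant/additional treatment given (yes/no) will be created".

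**The concern.** Treatment given for an adverse event is a safety result, and a reader will set Table 14.1.7 beside the adverse event tables and expect the same subjects in both. As planned, a dosed subject could have an event counted in Table 14.3.2.1 while the treatment for it is missing from Table 14.1.7, or the two tables could carry different denominators.

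The set matters most for injection site reactions and other non-systemic events. For these, Table 14.1.7 is the only planned summary that identifies treatment given. Systemic reactions have their own treatment-given summary in the Safety section.

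Table 14.1.2 ought to make any difference between the sets visible. Restricted to ITT, it cannot.

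**Working it through.** **Step 1: planned numbers (SAP section 5).** Total: 6 + 5 + 8 + 8 = 27, which reproduces the stated 27. Applying the ratios, and the actual 4 and 1 in cohort 2, DM-101 has 4 + 4 + 6 + 6 = 20 and placebo has 2 + 1 + 2 + 2 = 7. The DM-101 arms therefore hold four or six subjects.

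**Step 2: relation of the sets.** Safety = dosed. ITT = dosed and meeting the measurement condition. So ITT is contained in Safety, and the two differ by exactly those dosed subjects who fail the undefined minimum. Call that number k. The documents do not give k.

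**Step 3: effect on Table 14.1.7.** In an arm of n dosed subjects, let r be treated for an adverse event. On Safety the table shows r/n. With k = 1 (an assumption):

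- treated subject lost: (r − 1)/(n − 1), a change of −(n − r)/[n(n − 1)]
- untreated subject lost: r/(n − 1), a change of +r/[n(n − 1)]

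| n | r | Safety | Treated subject lost | Untreated subject lost |
|---|---|---|---|---|
| 6 | 1 | 1/6 = 16.7% | 0/5 = 0% (−16.7 points) | 1/5 = 20.0% (+3.3) |
| 6 | 2 | 2/6 = 33.3% | 1/5 = 20.0% (−13.3) | 2/5 = 40.0% (+6.7) |
| 6 | 3 | 3/6 = 50.0% | 2/5 = 40.0% (−10.0) | 3/5 = 60.0% (+10.0) |
| 4 | 1 | 1/4 = 25.0% | 0/3 = 0% (−25.0) | 1/3 = 33.3% (+8.3) |
| 4 | 2 | 2/4 = 50.0% | 1/3 = 33.3% (−16.7) | 2/4 becomes 2/3 = 66.7% (+16.7) |

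With k = 0 every entry equals the Safety column.

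**Step 4: direction.** If the lost subject is equally likely to be any of the n, the average change is {r × [−(n − r)] + (n − r) × r} / [n × n(n − 1)] = 0. A direction arises only if exclusion is linked to having been treated, and the documents do not establish such a link.

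**Step 5: Table 14.1.2.** Within ITT every subject is in ITT and, by step 2, also in Safety. Both counts equal the table's own denominator by construction, whatever k is. Only exclusions from the per protocol set could show.

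**The case against.** The strongest reply is that the two sets will probably coincide. In cohorts 3 and 4 each dosed subject stays about 6 h, with vital signs, FEV1, ECG, laboratory tests and injection site examinations (Protocol Tables 12 and 13). Subjects who stop dosing or withdraw are still asked for the follow-up safety assessments (Protocol 4.4 and 9.2). With no efficacy or pharmacokinetic assessments, a recorded reaction is already a relevant measurement on any ordinary reading. This stands as a statement of likelihood. It does not remove the mismatch, because the minimum is undefined and, outside section 14.1 of the table plan, ITT is used only for IgE and biomarkers. If the condition were read as needing a post-dose biomarker sample (an assumption), the first one scheduled is at Visit 3, day 14 (Protocol Table 11).

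Second, other outputs limit the loss. By-subject listings cover concomitant medication and adverse events, systemic reactions get narratives and a treatment-given summary, and unequal denominators would hint at an exclusion. This also stands, and it is why the point is minor. Listings are not a summary, however, and the treatment-given summary does not extend to non-systemic events.

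Third, placing demographics, history and medication on ITT is a common choice in a descriptive study. That is accepted: for Tables 14.1.3 to 14.1.6 the only gain is matching denominators.

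Three stronger readings are tempting and are not supported:

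- *That the error favours tolerability.* A reader might infer this by picturing a treated reactor being dropped. Losing an untreated subject raises the percentage, a placebo subject could be lost as well, and classification is completed before the code is opened.
- *That cohort 2 already shows such an exclusion.* Protocol Table 7 records one subject with "both withdrawal of consent and 2 Grade 3 local injection site reactions after 2 injections of IMP". Those reactions were graded, so post-dose data exist. Protocol 1.2.3 says follow-up of dosed subjects continued. Nothing says this subject was outside ITT or was treated.
- *That the effect can be expressed as 1/20, or 5 points, across all DM-101 subjects.* SAP section 10 reports medication by cohort and treatment group, so the pooled percentage is not a planned output.

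**Conclusion.** The point holds as an inconsistency in the assignment of analysis sets. Table 14.1.7 is a safety output placed on the only one of the two sets that can omit a dosed subject, and Table 14.1.2 cannot show whether that has happened.

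If one dosed subject of six falls outside ITT and one to three were treated, the Table 14.1.7 percentage moves by −16.7 to +10.0 points, with the sign depending on whether that subject was treated. If the sets coincide, the effect is nil. The sizes rest on the assumed k = 1 and on the planned arm sizes. The documents show no exclusion from ITT, and the classification of cohorts 1 and 2 is not available here.

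The primary endpoint is unaffected, because its tables are already on Safety. This is a minor, worthwhile correction.

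**What to change.** Before cohorts 3 and 4 are unblinded, make two changes in SAP 21.1:

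1. Run Table 14.1.7 on the Safety set, and name that set in SAP section 10.
2. Run Table 14.1.2 on all randomised subjects, showing by cohort and treatment how many are in Safety, ITT and per protocol.

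Optionally, run Tables 14.1.3 to 14.1.6 on Safety so that their denominators match the adverse event tables. The biomarker outputs can stay on ITT.

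The cost is a change of population labels and of the analysis-set filter in the programs. No new data are needed, and if the sets coincide the contents of Table 14.1.7 do not change.
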